### 3. Background

Chronic widespread pain (CWP), the cardinal feature of fibromyalgia, is associated with lost work productivity, psychological ill health, and poor quality of life. It is one of the most common reasons for referral to a rheumatologist (1). The cost of CWP is high in terms of both individual, societal and health costs: for example, in the United States, mean per-patient costs (including pain and non-pain-related medication, physician consultations, tests and procedures, and emergency department visits) in the 6 months following a new diagnosis of fibromyalgia have been reported as \$3481, comparable to patients with rheumatoid arthritis (2) but resulting in worse quality of life (3). Current guidelines recommend pharmacological, physical, and psychological therapies although the importance attributed to individual therapies is inconsistent (4). There is good evidence for musculoskeletal pain conditions generally that the longer the duration of symptoms, the less likely that symptoms are to improve (5, 6), including with specific interventions (7, 8). This is particularly so for CWP which, once developed, is challenging to manage and effect improvement.

A systematic review and meta-analysis of randomised controlled trials (RCT) of Cognitive Behaviour Therapy (CBT) for patients with fibromyalgia concluded that CBT improves coping with pain, reduces depressed mood and healthcare-seeking behaviour in such patients (9). The delivery of CBT by telephone has been shown to be effective, acceptable and accessible (10). The MUSICIAN study, which we have recently concluded, tested telephone delivered CBT (tCBT) and/or exercise for patients with chronic widespread pain consulting to their GP (using a 2 x 2 factorial design). Three months after the end of therapy, both interventions resulted in significantly better primary outcome measures (patient global health) than treatment as usual (tCBT 33% of participants with positive outcome, exercise 24%, treatment as usual 8%), but there was no significant additional benefit of receiving both interventions (combined 37%). Recent analyses have demonstrated these benefits are maintained 2 years after the end of therapy (11): tCBT 35% with positive outcome, exercise 29%, combined 31%, treatment as usual 13%. We have conducted a comprehensive literature review with the aim of identifying randomised trials which had the aim of preventing the onset either of CWP or fibromyalgia. This review did not identify any such published trials. Further, a search of 11 international clinical trials registers/databases (including US, UK, Europe, Australia/New Zealand, Japan), undertaken in Autumn 2013 did not identify any ongoing trial with the aim of preventing the onset of CWP (or fibromyalgia).

There are several reasons why it may be desirable to try to prevent CWP onset, namely that the majority of CWP patients do not have important symptom improvement with current management (even within trials). Prediction models from epidemiological studies have been developed to identify “high risk” patients, which makes such an approach feasible. Research using the General Practice Research Database (GPRD) has demonstrated that prior to receiving a diagnosis of fibromyalgia in primary care, persons have a long-term prior history of consultation with symptoms (12). Although this will be the first prevention trial in this area, the concept of prevention using CBT has been addressed in musculoskeletal disorders with respect to intervention in neck pain and low back pain before people become patients (13) and in mental disorders (14).

We have conducted prospective epidemiological studies which have demonstrated that it is possible to identify “high risk” groups. In the first study, a high risk group for CWP onset was identified on the basis of two factors: somatic awareness (using the Somatic Symptom Scale) and illness behaviour (using the Illness Behaviour Score) (15). This was replicated in a second study conducted by the applicants (16). These “aetiological models” excluded pain and therefore we have re-analysed data from the latter study (also considering pain status) to identify the best predictors of onset and which results in a model more suitable for use in prevention studies. The resulting “at risk model” requires regional pain and two of the following: maladaptive behavioural response to illness (Illness Behaviour score > 4), a high number of somatic symptoms (Somatic Symptom Score > 2) and sleep disturbance (Sleep Problem Scale Score > 4). In the second “validation” study, from a population of 2,374 persons without CWP, 653 satisfied the definition of “high risk of CWP” of whom 139 had developed CWP twelve months later (that is a Positive Predictive value of 21.3%). Amongst persons not deemed to be at high risk (n=1721), 77 developed CWP which is a Negative Predictive Value of 95.5%.

An Arthritis Research UK report on fibromyalgia/CWP, based on a think-tank held in July 2012, identified prevention as a research priority. We have previously shown short and long-term effectiveness of tCBT for CWP (compared to usual care), in an Arthritis Research UK funded study (11, 17). Specifically this demonstrated sustained improvement in patient global assessment of change, reduced psychological distress, fear of movement and reliance on passive coping styles. Secondly we have developed and refined statistical models which identify persons at high risk for the future development of CWP. We therefore now propose a study to test whether tCBT can reduce the risk of CWP onset amongst those at high risk.

#### **4. Objectives**

We will test the hypothesis that among patients who report regional pain for which they have already sought a consultation in primary care, and who are identified as high risk of developing chronic widespread pain, a short course of telephone-delivered Cognitive Behaviour Therapy (tCBT) reduces the onset of CWP.

We will further determine the cost-effectiveness of such a preventative intervention.

#### **5. Research Sites**

[figure not shown]
Three health boards in Scotland will be research sites for the study. The three health boards are NHS Grampian, NHS Highland, and NHS Greater Glasgow and Clyde. We will require the involvement of 7 or 8 equivalent general practices.

#### **6. Methods**

##### **6.1 Study design**

The study will be a two-arm randomised controlled trial testing a course of tCBT against usual care.

## 6.2 Timeline Flowchart

### **6.3 Recruitment**

We will mail a randomly selected sample of adults aged 25 years and over registered with participating general practices in the study areas.

The Scottish Primary Care Research Network (SPCRN) will be involved in recruitment of patients to this study from primary care. SPCRN staff provide GP practices with an expert service to undertake searches of their electronic databases to identify a random sample of potentially eligible patients and prepare the ethically approved letters to be sent out. SPCRN staff work on behalf of the healthcare team under practice staff supervision. Each member of SPCRN staff must have a current NHS substantive or honorary contract in order to carry out these activities. Searches are undertaken at each GP practice before the screening survey questionnaires are sent out by Health Informatics Centre Services in Dundee on behalf of the practice. Patients will return completed survey questionnaires to the research team at the University of Aberdeen where they will be assessed by the research team for eligibility and sent invitation letters if eligible.

The “screening questionnaire” will determine whether a) they meet the study eligibility criteria and b) they would be willing to be contacted again regarding a treatment trial for “musculoskeletal health”. The questionnaire will include:

- Pain assessed by specific questions on the experience of pain, consultation and body manikins (which will provide site and also allow us to exclude those who already have chronic widespread pain).
- Illness Behaviour Scale (18)
- Somatic Symptoms Scale (excluding pain items) (19)
- Sleep Problem Scale (20)
- Quality of Life and Wellbeing (EQ-5D-5L (21); ICECAP (22))
- General Health Questionnaire (23)
- Chalder Fatigue Scale (24)

The inclusion criteria are:

- A ‘high-risk’ profile for developing CWP as identified on the screening survey, i.e.:
  - Have pain for which they have sought consultation to primary care in the last 6 months, or have pain and report consulting a doctor frequently
  - Any 2 of the following:
    - Illness Behaviour Score > 4
    - Somatic Symptom Score > 2
    - Sleep Problem Score >= 4
- Access to a landline telephone or mobile telephone

- Ability to understand English sufficiently to participate in the intervention
- Ability to give informed consent
- Aged 25 years or over

Exclusion criteria:

- Meeting American College of Rheumatology definition of CWP in the 1990 criteria for fibromyalgia (as assessed by the screening questionnaire) (23)
- Medical conditions which would make the proposed intervention unsuitable (e.g. cognitive ability)

A list of eligible patients will be provided to the general practitioner in advance, with the option of indicating any as unsuitable for the study. Patients would then be sent information about the study and subsequently contacted by a member of the research team by telephone and, if appropriate, consented and recruited into the trial.

#### **6.4 Consent**

Included in the mailing to eligible patients will be an information sheet, consent form, best-time-to-call slip, and 4-item Pain Treatment Beliefs Questionnaire (24). Once a patient has returned a signed consent form and best-time-to-call slip, a member of the research team will phone them. The researcher will read out from a script giving information about the study, and the patient will have the opportunity then to ask questions about the study. If the patient consents to participate they will be recruited to the study and randomised to one of the arms of the trial. (It is only at this point that the participant is considered to have given informed consent).

#### **6.5 Randomisation**

After consent has been given to participate in the study the researcher will contact the Trial randomisation centre at the Centre for Healthcare Randomised Trials (CHaRT) at the University of Aberdeen, using the internet or by telephone. This service is available 24 hours a day. Using a computer randomisation program, subjects will be randomly allocated into one of the two treatment groups, stratified in blocks by one predictor of outcome i.e. the number of non-pain “high-risk” factors they report (2 or 3) since this is related to the risk of CWP onset, and GP Practice. Subjects will be notified of the outcome of allocation during the consent/randomisation phone-call. If allocated to the active intervention, the participant will receive a phone call from a therapist within 3 working days to arrange an initial appointment. We will confirm the allocation to treatment arm in a letter to the participant.

#### **6.6 Follow Up**

Follow-up questionnaires will be mailed to participants at 3, 12 and 24 months after the treatment start date (for participants in the active treatment group) or dummy treatment start date (for those in usual care). Instruments included in the follow-up questionnaires will be the same as in the screening survey questionnaire. Additionally, follow-up questionnaires will include the Patient Global Impression of Change (7-item scale from “very much worse” to “very much better”), questions on health care usage,

and the Pain Treatment Beliefs Questionnaire (24). At 3-month and 12-month follow-up time-points, participants who do not return a questionnaire will receive a reminder telephone call, and those uncontactable by telephone will be sent a shortened one-sheet version of the follow-up questionnaire. At the 24-months follow-up time-point, participants who do not return a questionnaire will be telephoned and asked some questions over the phone (date of birth, Patient Global Impression of Change, and whether they have pain at specific sites and for how long), and those uncontactable by telephone will be sent the shortened one-sheet version of the questionnaire.

### **Cohort Follow-up**

In order to examine the effects of selection bias and the effects of being randomised into a trial a cohort of participants who were eligible and gave consent to be contacted for future health surveys but either did not consent to an invitation letter, or were invited but not recruited to the trial will also be followed-up to collect main outcome data.

A questionnaire will be sent 66 weeks after the date of completion of the screening survey questionnaire (to match the average length of time between screening survey completion and 12-month follow-up for trial participants) to those matching the following criteria:

- A 'high-risk' profile for developing CWP as identified on the screening survey, i.e.:
  - Have pain for which they have sought consultation to primary care in the last 6 months, or have pain and report consulting a doctor frequently
  - Any 2 of the following:
    - Illness Behaviour Score > 4
    - Somatic Symptom Score > 2
    - Sleep Problem Score >= 4
- Gave consent to be contacted for future health surveys
- Were not recruited to the MAMMOTH trial
- Provided name and address details

The questionnaire will collect the following information:

- Demographic information (age, gender, employment status)
- Self-reported change in overall health
- Pain assessed by manikin, and chronicity
- The Sleep Problem Scale
- Illness Behaviours Scale
- Somatic Symptoms Scale

The questionnaire will be sent with a covering letter, and reminders will be sent to the same schedule as in the main trial.

### **6.7 Acceptability sub-study**

Participants assigned to the CBT group who complete their treatment, will be invited to participate in an acceptability sub-study. The purpose of the sub-study is to explore participants' experience of treatment

with a view to understanding influences on acceptability of the intervention. Interviews will be conducted by telephone. The protocol for this sub-study will be a separate document.

### **6.8 Newsletter Sub-study**

Before participants reach the 24-month questionnaire timepoint, half will be randomly assigned to receive a participant newsletter. The purpose of this is to examine the effect of receiving such a newsletter on follow-up rates. The newsletter will contain an update on the progress of the study (e.g. recruitment numbers, follow-up timeline, participating regions) with a stress on the importance of participation in studies.

### **6.9 CONTAIN Sub-study**

Trial participants who have not withdrawn from receiving further follow-up questionnaires and who have not been marked as deceased, will be invited to participate in a sub-study looking at the effects of the COVID-19 pandemic and the associated 'lockdown' measures on their health and healthcare needs. The protocol for this study, the CONTAIN Study, and participant documents are an appendix to the main MAmMOTH Study protocol.

## **7. Treatment Protocol**

The CBT intervention, delivered by telephone, will consist of an initial assessment (45-60 minutes), 6 weekly sessions (each 30-45 minutes) over six weeks, and then booster sessions at 3 and 6 months. The intervention will be delivered by therapists trained for the study and accredited by the British Association for Behaviour and Cognitive Psychotherapies (BABCP). Participants will be supported by a self-management CBT manual refined from the manual we developed for the MUSICIAN study where it was successfully used with demonstrable patient benefit.

There will be a patient-centred assessment by the therapist for problem identification, risk assessment and development of a shared formulation of the current health problem. The sessions will involve education about musculoskeletal pain (all persons will have recently consulted to primary care with regional pain), somatic symptoms and specific CBT techniques such as pacing of activity, behavioural activation, diary keeping, identifying and challenging negative and unhelpful thinking patterns and the development of a longer term management plan. Participants' self-management manuals will include agreed collaborative goals for the therapist and patient to work towards, diaries, some example patient stories and some exercises to complete after specific sessions. Participants and therapists will be asked to complete the 5-item Agnew Relationship Measure after the sixth of the weekly sessions (25).

Therapists delivering the intervention will receive a 2 day training programme conducted by two of the investigators, KL and JM. Therapists will also be asked to complete the Pain Treatment Beliefs Questionnaire (24). Therapists will be supervised two weekly throughout the trial period. Patient adherence will be examined through collecting data on number of telephone consultations conducted and evaluation of the use of CBT techniques through exercises contained in the manual.

The group allocated to usual care will receive no additional intervention – this will reflect the fact there is no specific intervention provided to patients currently for the prevention of CWP. They will receive

usual care and there will be no restriction on what this can involve. CBT is not readily available within the NHS and is generally restricted to persons who have developed specific conditions rather than persons at risk of those conditions. We will however monitor care received, outwith the trial, in all participating subjects, and health care usage will be recorded in follow-up.

## **8. Patient Safety**

There are unlikely to be major safety issues in terms of delivery of the CBT. However, if the therapists delivering CBT have any concerns, one of the investigators will be available to assess these. There will be a standard template for reporting concerns and recording of any action recommended. This will be overseen by the investigator, KL.

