Table 19: Secondary outcome adjusted analysis of QoL from ICECAP score in the tCBT and usual care arms on the ITT population

	3 Months			12 Months			24 Months		
	Adjusted coefficient	95% CI	p-value	Adjusted coefficient	95% CI	p-value	Adjusted coefficient	95% CI	p-value
Treatment: tCBT vs Usual care									
QoL from ICECAP score at baseline									
Number of high-risk factors present: 3 vs 2									
Age									
Gender									
Random effect: GP practice									

Table 20: Secondary outcome adjusted analysis of Fatigue score in the tCBT and usual care arms on the ITT population

	3 Months			12 Months			24 Months		
	Adjusted coefficient	95% CI	p-value	Adjusted coefficient	95% CI	p-value	Adjusted coefficient	95% CI	p-value
Treatment: tCBT vs Usual care									
Fatigue score at baseline									
Number of high-risk factors present: 3 vs 2									
Age									
Gender									
Random effect: GP practice									

Table 21: Secondary outcome adjusted analysis of Global impression of change measure score in the tCBT and usual care arms on the ITT population

	3 Months			12 Months			24 Months		
	Adjusted coefficient	95% CI	p-value	Adjusted coefficient	95% CI	p-value	Adjusted coefficient	95% CI	p-value
Treatment: tCBT vs Usual care									
Global impression of change measure score at baseline									
Number of high-risk factors present: 3 vs 2									
Age									
Gender									
Random effect: GP practice									

Table 22: Primary outcome presence of CWP at 3, 12 and 24 months in multilevel model in the tCBT and usual care arms on the ITT population

	Multilevel at 3 time points		
	Adjusted OR	95% CI	p-value
Treatment: tCBT vs Usual care			
3 to 12 months			
12 to 24 months			
Number of high-risk factors present: 3 vs 2			
Age			
Gender			
Random effect: GP practice			

Table 23: Secondary outcome presence of pain at 3, 12 and 24 months in multilevel model in the tCBT and usual care arms on the ITT population

	Multilevel at 3 time points		
	Adjusted OR	95% CI	p-value
Treatment: tCBT vs Usual care			
3 to 12 months			
12 to 24 months			
Number of high-risk factors present: 3 vs 2			
Age			
Gender			
Random effect: GP practice			

Table 24: Secondary outcome illness behaviour score at 3, 12 and 24 months in multilevel model in the tCBT and usual care arms on the ITT population

	Multilevel at 3 time points		
	Adjusted coefficient	95% CI	p-value
Treatment: tCBT vs Usual care			
3 to 12 months			
12 to 24 months			
Illness behaviour score at baseline			

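### Dedicated safety reporting exists only in the tCBT arm, and the SAP plans no by-arm count of participants who got worse, although both arms supply the data

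*Protocol*

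**What the plan says.** Protocol section 8 (Patient Safety) makes one provision for detecting harm. It says that "if the therapists delivering CBT have any concerns, one of the investigators will be available to assess these", and adds: "There will be a standard template for reporting concerns and recording of any action recommended". It defines no adverse event, sets no time window and describes no equivalent in the control arm. Section 7 says: "The group allocated to usual care will receive no additional intervention". Therapist contact in the active arm is an initial assessment, then "6 weekly sessions (each 30-45 minutes) over six weeks, and then booster sessions at 3 and 6 months".

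Section 6.6 follows both arms at 3, 12 and 24 months. It repeats the screening instruments, which include the General Health Questionnaire (GHQ), and adds the "Patient Global Impression of Change (7-item scale from “very much worse” to “very much better" and questions on health care use. Under section 9, people who leave treatment still receive questionnaires unless they ask not to.

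The SAP has no safety section and no harms table. Table 7 summarises global change and GHQ distress as medians (IQR). Table 21 is a "Secondary outcome adjusted analysis of Global impression of change measure score in the tCBT and usual care arms", giving one treatment coefficient per time point; Table 17 does the same for distress. Table 33 gives withdrawals from the study, with the primary reason, by arm.

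Protocol section 6.7 sets the interview invitation: "Participants assigned to the CBT group who complete their treatment, will be invited to participate in an acceptability sub-study". It refers to a separate sub-study protocol.

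**The concern.** A therapist-based route gives reports from one arm with nothing to set beside them. It also depends on contact, so it is weakest for people who leave therapy early, and some of them may have left because they felt worse. The interviews, as section 6.7 describes them, lean the same way.

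The questionnaires do cover both arms for the full 24 months, but the planned summaries describe the centre of the distribution. A therapy can help most recipients a little and set some back. A reader of the trial report would want to know how many got worse in each arm. That matters here because the intervention is offered to people who do not yet have the condition it aims to prevent.

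**Working it through.** **Step 1. Set the sources side by side.**

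| Source | tCBT | Usual care | Period | By-arm output in the SAP |
|---|---|---|---|---|
| Therapist concern template (Protocol 8) | yes | no | while in contact; last scheduled contact at 6 months | none |
| Global change (Protocol 6.6) | yes | yes | 3, 12, 24 months | median (IQR) in Table 7; treatment coefficient in Tables 21 and 31 |
| GHQ distress (Protocol 6.3, 6.6) | yes | yes | screening, 3, 12, 24 months | median (IQR) in Table 7; treatment coefficient in Table 17 and in the multilevel tables |
| Health care use (Protocol 6.6, 7) | yes | yes | follow-up | none |
| Withdrawal from the study, with reason (SAP 2.5) | yes | yes | whole study | Table 33 |
| Reason for stopping tCBT | not tabulated | not applicable | – | Table 5 shows treatment completed, no or yes, without a reason |

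Someone who stops tCBT because they feel worse but goes on returning questionnaires is not a study withdrawal under Protocol section 9 or SAP section 2.5. That person's reason appears in no planned table.

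**Step 2. What the planned summaries can hide.** The quartile on the worse side is set by the worst 25% of an arm. If fewer than 25% fall in the worst categories, neither that quartile nor the median need move. As an illustration, arms with 5% and 20% in those categories could show the same median and IQR in Table 7.

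A linear coefficient on the category score can cancel in the same way. Suppose the extra 20 − 5 = 15 in every 100 each drop two categories while 30 in every 100 others each rise one. The change in the mean is −0.15 × 2 + 0.30 × 1 = 0. An ordinal model uses every category but still reports one common effect.

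**Step 3. Number analysed.** The documents give no figure for harm, so the planned sample size sets the scale. Inputs (Protocol section 10; SAP 1.4 and 2.4.1): 21% versus 12%, 90% power, two-sided 5%, 80% return. The two-proportion formula with continuity correction gives 378 per arm, and 378 / 0.80 = 472.5, rounded up to 473. This reproduces the plan's 473 exactly. Without the correction it is 356 / 0.80 = 445, which does not match. The number analysed per arm is therefore 473 × 0.80 ≈ 378.

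**Step 4. Precision of a by-arm proportion worse.** The proportion who worsen is not in the documents, so a range of 5% to 30% is assumed. Half-width of the 95% CI for the difference = 1.96 × √(2p(1 − p)/378):

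- p = 0.05: 1.96 × √(0.095/378) = 0.031
- p = 0.10: 1.96 × √(0.18/378) = 0.043
- p = 0.30: 1.96 × √(0.42/378) = 0.065

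Over the same range, the excess detectable with 80% power is about 5.5 to 9.7 points at two-sided 0.05, and 7.0 to 12.0 points at the SAP's 0.01 for secondary outcomes.

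These figures fit global change best. At 24 months section 6.6 has non-returners asked about global change by telephone, but does not list the GHQ among those questions, so GHQ numbers may be lower.

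**Step 5. Who is outside the interviews.** SAP section 2.1 counts treatment as complete after at least three sessions including the assessment, or after the assessment alone if therapist and participant agree to stop. If section 6.7 uses that definition, the people left out are those with fewer than three sessions and no mutual agreement. A stricter meaning would leave out more.

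**The case against.** A reader might infer that the trial cannot say whether tCBT made anyone worse, or that nothing bearing on harm is compared by arm. The documents do not support that. The SAP compares CWP, pain, illness behaviour, somatic symptoms, sleep, distress, EQ-5D, ICECAP, fatigue and global change between arms at all three times, with two-sided tests. With 378 per arm, the CWP comparison alone has about 81% power (no continuity correction) to show a rise from 21% to 30%. This stands: average worsening would be visible, and the gap is limited to a minority hidden within an acceptable average.

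It is also fair to say that no text states that the therapist route closes when someone stops tCBT. That is an inference from its dependence on contact. Study withdrawals and their reasons are tabulated in both arms, though Step 1 shows what that table leaves out.

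On the interviews, the SAP's completion rule is lenient, so many early stoppers remain eligible. The sample-size section assumes 75% adherence, and it is tempting to read the other quarter of the tCBT arm as excluded. Adherence is not defined there and need not equal completion, so the number excluded cannot be derived. The separate sub-study protocol was not available and may handle non-completers differently.

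Deaths are another tempting inference. Section 6.9 excludes from the sub-study invitation anyone not among those "who have not been marked as deceased". That shows some deaths become known to the team, not that they are collected systematically or equally by arm.

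Finally, Step 4 measures the precision of the proposed table. It does not measure harm missed.

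**Conclusion.** The point holds in a limited form. Dedicated safety reporting is confined to the tCBT arm and to the period of therapist contact. The SAP would detect average worsening but specifies no by-arm count of people who deteriorated. The stated interview invitation leaves out at least those who stopped before three sessions without mutual agreement, if the SAP definition of completion applies.

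The data for a by-arm count are already collected. They would give a 95% CI of roughly ±3 to ±6.5 points, assuming 5% to 30% worsen and the planned 80% return. The primary result and sample size are not affected. This is an inexpensive improvement to what the trial can report, and it does not imply that tCBT is harmful.

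**What to change.** 1. Add one descriptive table to the SAP, by arm at 3, 12 and 24 months, for all randomised participants with data at that time. It should give:
   - the percentage in the worsened categories of global change, with the cut-point fixed before any unblinded analysis;
   - the percentage whose GHQ score is worse than at screening by a threshold fixed in advance;
   - risk differences with 95% CIs for both;
   - known deaths by arm, described as known rather than systematically collected;
   - therapist concern reports, as a tCBT-only line marked as having no comparator.
2. In Protocol section 6.7, and in the separate sub-study protocol if it carries the same restriction, invite tCBT participants who stopped treatment as well as completers, within the same number of interviews.

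The cost is one table from data already held and one sentence in section 6.7. The downsides are a few more descriptive comparisons, which should be read as estimates and not tests, and fewer completers interviewed.
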